#### 6.3.5. On-Treatment Period

The on-treatment period starts on the date of the start of study treatment and ends 28 days after the end of study treatment (including dose taper period).

Within the on-treatment period, there are two distinct treatment periods:

- Double-blind on-treatment period starts on the date of the start of study treatment and ends
  - 28 days after the end of study treatment, for subjects who discontinue study treatment during the Double-blind Period of the study
  - Before the start of the OLE treatment period, for subjects who continue onto the OLE Period of the study

• OLE on-treatment period applies only to subjects who complete the Double-blind Period of the study, and starts with the first dose of open-label mitapivat in the OLE Period and ends 28 days after the end of study treatment

For subjects who receive mitapivat in the OLE Period, assessments or events occurring on the date of first dose of mitapivat in the OLE Period will be included in the analysis of the data from the double-blind on-treatment period, except for AEs and concomitant medications reported for subjects in the placebo arm which will be included only in the analysis of the data from the OLE on-treatment period.

Data listings will include all assessments and events, with those that occur outside of the on-treatment period flagged.

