8.7. Red Blood Cell Transfusions

All HRQOL assessments and the 6-minute walk test (6MWT) (see Section 8.11) must be conducted before all other study visit assessments, including blood sampling. All blood samples must be collected before administration of the study drug and before the RBC transfusion, if an RBC transfusion is scheduled on the same day.

Transfusion history will be recorded for the 24-week period before randomization. On-treatment transfusions will also be recorded. The transfusion history and on-treatment transfusion record includes transfusion dates, number of RBC units transfused, and pretransfusion Hb concentration. An RBC unit refers to packed red blood cell (pRBC) preparations. Due to hematocrit concentration differences in blood products used per local standards of care, 2 units of whole blood are equivalent to 1 unit of pRBCs and constitute an RBC unit. If available, the volume and the hematocrit of each transfused RBC unit should also be recorded. All RBC transfusions, including those received outside of the clinical study center, must be recorded.

Subjects may receive RBC transfusions at the discretion of the Investigator as clinically indicated.

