10.4.1.2. On-Treatment Period

The on-treatment period begins on the date of the start of study drug and ends 28 days after the end of study drug administration (including the recommended dose taper).

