#### 6.3.2. Start and End Dates of Study Treatment

The start of study treatment is the earliest date/time of administration of a non-zero dose of the study drug.

The end of study treatment is the latest date/time of administration of a non-zero dose of the study drug on or before the EODB period date/ EOS date.

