#### **Safety Evaluations**

For clinical laboratory assessments the following applies:

- Before deriving the baseline:
  - If there are multiple records with the same assessment day and time from the same laboratory, the average value will be used.
  - If there are multiple records with the same assessment day and time from different laboratories, the value from the central laboratory will be used.
- The baseline will then be the last value before the start of study treatment.

For all other safety parameters, the last assessment before the start of study treatment will be used as the baseline.

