### Parameters with CTCAE grades available:

Clinical laboratory test results will be graded according to CTCAE v4.03 as applicable. Grading will be derived based on the numerical thresholds defined by the CTCAE criteria. Non-numerical qualifiers will not be taken into consideration in the derivation of CTCAE grading.

Laboratory test results classified according to CTCAE will be described using the worst grade. For parameters graded with 2 separate toxicity criteria, such as potassium (hypokalemia/hyperkalemia), the toxicities will be summarized separately. Low direction toxicity (eg, hypokalemia) grades at baseline and postbaseline will be set to 0 when the variables are derived for summarizing high direction toxicity (eg, hyperkalemia), and vice versa.

The frequency of subjects with laboratory toxicities during the on-treatment period will be tabulated as follows. The denominator used to calculate percentages for each laboratory test is the number of subjects evaluable for CTCAE grading for that parameter (ie, those subjects for whom a Grade of 0, 1, 2, 3 or 4 can be derived).

- The summary of laboratory parameters by CTCAE grade will include the number and percentage of subjects with Grade 1, 2, 3, 4; Grade 3-4; and Any Grade (Grades 1-4) during the on-treatment period. The highest CTCAE grade during the on-treatment period is considered the worst grade.
- The shift table will summarize baseline CTCAE grade versus worst CTCAE grade during the on-treatment period. The highest CTCAE grade during the on-treatment period is considered the worst grade.
- Newly occurring or worsening laboratory abnormalities (Any Grade, Grade 3-4) during the on-treatment period will also be summarized.

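### In the double-blind CTCAE laboratory tables, a pre-dose Day 1 value counts as both baseline and on-treatment, so the shift table cannot show improvement from a Day 1 baseline and the worst-grade counts include pre-drug abnormalities

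*SAP*

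**What the plan says.** **Start of the on-treatment period.** SAP 6.3.5: "The on-treatment period starts on the date of the start of study treatment". Protocol 10.4.1.2 agrees: "The on-treatment period begins on the date of the start of study drug". Both work by calendar date.

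**Start of treatment and baseline.** SAP 6.3.2 is finer: "The start of study treatment is the earliest date/time of administration of a non-zero dose of the study drug". The laboratory safety baseline in SAP 6.3.4.1 depends on that moment: "The baseline will then be the last value before the start of study treatment".

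**Day 1 samples.** Protocol Table 1 schedules hematology, clinical chemistry, liver tests with LDH, and sex hormones on Day 1. Protocol 8.7 fixes their timing: "All blood samples must be collected before administration of the study drug". Where times are missing, SAP 6.3.4.1 assumes that an assessment planned for Day 1 before dosing was taken before dosing.

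**Laboratory tables.** SAP 7.7.3, for parameters with CTCAE grades: "The shift table will summarize baseline CTCAE grade versus worst CTCAE grade during the on-treatment period", and "The highest CTCAE grade during the on-treatment period is considered the worst grade". A frequency table by grade uses the same worst grade. SAP 7.7.3.2 categorizes ratios to ULN for ALT, AST, ALP and total bilirubin over the on-treatment period. Shift tables for ungraded parameters and for sex hormones (7.7.3.3) go to each of the low, normal and high categories, with no worst-value rule. SAP 7.7.3 adds: "Newly occurring or worsening laboratory abnormalities (Any Grade, Grade 3-4) during the on-treatment period will also be summarized".

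**The concern.** Baseline is resolved by date and time, but the on-treatment period only by date. The Day 1 pre-dose sample falls on both sides of that line, and it is the scheduled baseline draw for most safety laboratory parameters.

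A table of baseline grade against worst on-treatment grade is meant to show what happened after dosing. If the baseline record is also a candidate for the worst value, the improving cells are empty by construction. A subject who entered with a Grade 3 value that resolved on treatment is reported as having an on-treatment Grade 3 toxicity. A reader of the study report could take pre-existing disease for events under study drug. This matters more than usual here because Hb and bilirubin are abnormal at entry in this population and are expected to improve on mitapivat.

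The same gap reaches the worst-value and worst-change summaries in SAP 6.4.5, which include vital signs. Day 1 vital signs are taken before blood sampling, so they too are pre-dose.

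**Working it through.** The documents give no figure to reproduce; the check is one of logic, followed by an illustration of size.

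**Step 1. Is the overlap removed elsewhere?**
- The analysis visit windows in SAP 6.4.5 start on study day 2, but apply only to efficacy endpoints and bone mineral density.
- SAP 6.3.5 settles the same-day problem for the open-label extension: that period starts with the first open-label dose, and assessments on that date go to the Double-blind Period (apart from placebo-arm adverse events and concomitant medications). There is no matching rule for the double-blind start.
- SAP 7.7.3 does not require the worst grade to come from a post-dose record.

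So nothing removes it for the double-blind laboratory tables.

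**Step 2. Exact consequence for graded parameters.** Let b be the Day 1 baseline grade (0 to 4) and k the number of scheduled double-blind post-dose draws. From Table 1, k = 2 for chemistry (Weeks 12 and 24) and k = 6 for hematology and liver tests (Weeks 4 to 24). There are 5^(k+1) possible grade sequences.
- Literal rule: worst = max(b, post-dose grades), which is at least b.
- Post-dose rule: worst = max(post-dose grades).

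| Sequences | Formula | k = 2 | k = 6 |
|---|---|---|---|
| All | 5^(k+1) | 125 | 78,125 |
| Can show improvement, literal rule | none | 0 | 0 |
| Can show improvement, post-dose rule | 1^k + 2^k + 3^k + 4^k | 30 | 4,890 |
| Grade 3-4 only because of the Day 1 value | 2 × 3^k | 18 | 1,458 |
| New or worsening, either rule | 5^(k+1) − (1^k + 2^k + 3^k + 4^k + 5^k) | 70 | 57,610 |

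These count possible patterns, not expected patients. The zero is exact. The last row shows that the newly-occurring-or-worsening summary is the same under both rules.

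**Step 3. Size, by illustration.** All inputs are assumptions: true Hb mean 8.1 and SD 1.1 g/dL, truncated at 10; within-subject SD 0.3; six post-dose visits; a cut at 8.0 g/dL standing in for a grade boundary; 400,000 simulated subjects.

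| True shift | Ever below cut, Day 1 excluded | Day 1 included | Below cut at baseline and shown improved, Day 1 excluded | Day 1 included |
|---|---|---|---|---|
| 0 (placebo) | 62.6% | 63.5% | – | 0% |
| +0.5 g/dL | 44% | 52% | 16% | 0% |
| +1.0 g/dL | 27% | 49% | 45% | 0% |

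With a within-subject SD of 0.5, the 45% becomes 34%. The difference between arms falls from 62.6 − 44 ≈ 19 to 63.5 − 52 ≈ 12 points at +0.5, and from 62.6 − 27 ≈ 35 to 63.5 − 49 ≈ 15 points at +1.0.

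For scale, Protocol 2.1.2.3.2 reports a mean Phase 2 Hb increase of 1.3 g/dL over Weeks 12 to 24. The sample size assumes a 35% response rate at a 1.0 g/dL threshold. A uniform +1.0 shift puts the mean change on that threshold, so about 50% respond, which is more optimistic than the plan. With the shift set to give about 35% responders, including Day 1 adds 16 to 18 points in the mitapivat arm.

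**Step 4. Tables outside the effect.**
- Open-label extension shifts: in both arms the baseline precedes the first open-label dose.
- DXA shifts: on-study scans are scheduled only in the extension.
- Lipids: no Day 1 draw; screening and Week 24 only in the Double-blind Period.
- Ungraded and sex-hormone shifts: a subject high on Day 1 and normal later can appear under normal, although the baseline category may also be counted as on-treatment.
- By-visit summaries: Day 1 does not enter later visits.

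**The case against.** The best defense is that the intent is clear. SAP 6.3.2 defines the start of treatment by date and time, SAP 6.3.4.1 sorts Day 1 assessments into before and after dosing, and the CTCAE text in SAP 7.7.3 speaks once of grades at baseline and postbaseline. A programmer might well use only post-dose records. But the postbaseline remark concerns parameters graded in two directions and does not redefine worst grade, and the sorting of Day 1 assessments serves the baseline derivation. The rule actually stated is the highest grade in a period that opens on a calendar date. Literal programming follows that rule.

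Second, the harm is limited, and this stands. Adding Day 1 can only add counts, so no post-dose toxicity is lost. The newly-occurring-or-worsening table is intact. Improvement in Hb and indirect bilirubin is assessed in dedicated efficacy analyses whose windows start on study day 2.

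Third, the illustration rests wholly on assumed inputs, and the +1.0 g/dL row is favorable to the concern. This also stands, so a range is given.

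A reader might infer that no shift table in the study can show improvement, or that every subject is affected. The documents do not support either: Step 4 lists tables that escape, and a subject with no Day 1 sample has a screening baseline outside the period. Nor do they support calling the between-arm laboratory comparison wrong as a whole. The rule is identical in both arms, and the treatment-emergent and by-visit comparisons are unaffected.

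**Conclusion.** The defect is real and limited to the Double-blind Period, for dosed subjects and parameters with a pre-dose Day 1 sample. Read literally, the CTCAE shift table cannot show improvement from a Day 1 baseline; that follows exactly from the text. The CTCAE worst-grade frequency and ULN-ratio tables count abnormalities present before any drug, and ungraded and sex-hormone shifts may do so too.

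The effect on the comparison between arms depends on how far values move. Under the stated assumptions the mitapivat count rises by 8 points at +0.5 g/dL (52 − 44) and 22 points at +1.0 g/dL (49 − 27), against about 1 point on placebo. The direction follows from the rule whenever one arm improves more; the size is illustrative and should not be quoted as an expected result. With no drug effect, only the absolute counts are inflated, apart from chance imbalance at baseline.

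Primary and key secondary endpoints, type I error and power are untouched. It should still be corrected, because a stated rule yields misleading safety tables and the correction is trivial.

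**What to change.** In SAP 6.3.5 and 7.7.3, and in Protocol 10.4.1.2, state that on-treatment worst-value, worst-grade, ULN-ratio and shift summaries for laboratory tests and vital signs use only assessments after the date/time of first dose. Add that Day 1 assessments scheduled before dosing, and any record used as baseline, are excluded from these summaries. Where the time is missing, the existing assumption in SAP 6.3.4.1 can decide the side on which a Day 1 record falls. Keep the date-based start for adverse events.

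The cost is one sentence in each document and one programming condition. No new data are needed, and no efficacy analysis changes.

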## 6.4. General Methods

#### 6.4.1. Data Handling After End of Double-blind Period

Data after the EODB period may not undergo the cleaning process and will not be displayed in any listings or used for summary statistics, statistical analyses, or imputations for the primary CSR.

#### 6.4.2. Standard Derivations and Reporting Conventions

The following conversion factors will be used to convert days into weeks, months or years: 1 week=7 days, 1 month=30.4375 days, and 1 year=365.25 days.

The following derivations will be implemented.

• Age (years) = (date of informed consent-date of birth+1)/365.25

If only day of birth is missing: Age (years): (year/month of informed consent-year/month of birth)

If day and month of birth are missing: Age (years): (year of informed consent-year of birth)

The integer part of the calculated age will be used for reporting purposes.

- Body mass index (BMI, kg/m^2)=weight (kg)/height (m)
- Duration (in days) from a reference date (eg, randomization date, start date of study treatment) =

date of event-reference date + 1, if the date of the event is on or after the reference date

date of event-reference date, if the date of the event is before the reference date

Reporting conventions will be as follows:

• Mean (including arithmetic mean and geometric mean) and median will be displayed to one more decimal place than the raw data.

- Standard deviation (SD) will be displayed to two more decimal places than the raw data.
- Percentages (including percent changes from baseline for whole blood concentration of 2,3-DPG and ATP, relative standard deviation [RSD%], arithmetic coefficient of variation [CV%], and geometric coefficient of variation [CV% geometric mean]) will be displayed to 1 decimal place (however, percentages corresponding to 0 counts will be reported as 0 rather than 0.0 and 100 percent will be reported as 100 rather than 100.0).
- p-values will be reported with 4 decimal places; all p-values should be specified to be 1-sided or 2-sided.
- Unless otherwise specified, rounding will be performed to the closest integer/first decimal using the common mid-point between the two consecutive values, eg, 5.11 to 5.14 will be rounded to 5.1, and 5.15 to 5.19 will be rounded to 5.2.
  - Non-zero percentages that are <0.1 before rounding will be displayed as "<0.1", eg, 0.09 will be reported as <0.1 rather than as 0.1.
  - p-values<0.0001 before rounding will be displayed as "<0.0001", eg, a

     p-value of 0.00009 will be displayed as <0.0001 rather than as 0.0001.

- PK parameters will be reported to 3 significant figures, except for  $T_{max}$  and  $T_{last}$  which will be reported to 2 significant digits.

Note that some PK parameters are observed values (eg,  $C_{max}$ ), while other PK parameters are derived from the intensive PK profiles (eg, AUC0-last). For all the PK parameters, regardless of whether they are observed or derived, the individual PK parameter values are considered "raw data" when implementing the above reporting rules.

## 6.4.3. Pooling of Data Across Sites

In order to provide overall estimates of treatment effects, data will be pooled across sites. The "site" factor will not be considered in statistical models or subgroup analyses given the high number of participating sites in contrast to the anticipated small number of subjects randomized at each site.

## 6.4.4. Continuous and Categorical Variables

Continuous variables will be summarized using descriptive statistics, ie, number of nonmissing values, mean, SD, median, quartiles, minimum, and maximum. PK concentrations and parameters will be further summarized using arithmetic mean together with the CV% and 90% CI, geometric mean together with CV% geometric mean and 90% CI. PD concentration and parameters will be further summarized using arithmetic mean together with the CV% and 95% CI, geometric mean together with the CV% and 95% CI, and RSD% (applicable to PD concentration only).

Categorical variables will be summarized by frequency distributions (number and percentage of subjects within a given category in the analysis data set). Unless otherwise specified, the calculation of percentages will include the "missing" category. Therefore, counts of missing observations will be included in the denominator and presented as a

separate category. For summaries by visit, percentages will be based on the number of subjects with data available for that visit, unless otherwise specified.

#### 6.4.5. Unscheduled Visits

Generally, data collected at unscheduled visits will be included and summarized for both safety and efficacy analyses in the same manner as the data collected at scheduled visits. PK and PD data collected at unscheduled visits will be listed and may not be summarized. Descriptive statistics (mean, SD, median, quartiles, minimum, and maximum) by nominal visit or time point for safety endpoints such as clinical laboratory measurements and vital signs will include only data from scheduled visits.

Summaries of outliers (eg, worst value, worst change from baseline, worst Common Terminology Criteria for Adverse Events [CTCAE] grade) during the on-treatment period for safety endpoints such as AEs, vital signs, and clinical laboratory measurements will include data from both scheduled and unscheduled visits.

For efficacy endpoints (Section 7.6), BMD by DXA scan (Section 7.7.5), data collected at unscheduled and scheduled postbaseline visits will be mapped to scheduled visits using analysis visit windows, and then values at scheduled postbaseline visits will be derived based on the rules described below. Descriptive statistics by nominal visit and longitudinal plots will be provided using the derived values at scheduled visits.

#### **Analysis Visit Windows**

For the evaluation of efficacy endpoints (Section 7.6),

and BMD by DXA scan (Section 7.7.5), the analysis visit windows will be derived based on the target study day for the scheduled visits as follows. Note that based on the schedule of assessments, a Week 4 Visit, for example, will have a target study day of  $1+(4\times7)=29$ .

For the Double-blind Period:

- Visit windows will be implemented for scheduled visits after study day 1 (ie, starting at Week 4 through the end of the Double-blind Period on Week 24).
- For analysis visit(n):
  - Start day of visit window =1+end day of window for visit(n-1). If n=1, start day of the visit window is study day 2
  - End day of visit window = [(target day for analysis visit(n) + target day for analysis visit(n+1))/2]-1 for Week < 24. The end day of visit window for Week 24 is the end of the Double-blind Period

  - Not applicable to DXA scan results which are only scheduled in the OLE Period.

For the OLE Period:

• Visit windows will be implemented for all scheduled visits after the first dose of mitapivat in the OLE Period. Week 288 is the last scheduled visit in the OLE Period.

- For analysis visit(n):
  - Start day of visit window = 1+ end day of window for visit(n-1). If n=1, start day of the visit is the day after the first dose of mitapivat in the OLE Period.
  - End day of visit window = [(target day for analysis visit(n) + target day for analysis visit(n+1))/2]-1 for Week < 288. The end day of visit window for Week 288 is the EOS date.

#### Derivation of Values at Scheduled Postbaseline Visits Based on Analysis Visit Windows

For laboratory parameters associated with efficacy endpoints (Section 7.6),

if multiple assessments are identified within a visit window for a

#### parameter, then

- Central laboratory assessment(s) (scheduled or unscheduled) within the visit window will be used
- If no central laboratory value is within the visit window, local laboratory assessment(s) within the visit window will be used

For the evaluation of efficacy endpoints (Section 7.6), and BMD by DXA scan (Section 7.7.5), if multiple assessments are identified within a visit window for a parameter and after selecting the assessments for laboratory parameters as described above, the following rules will be applied:

- The assessment measured closest to the target study day of the scheduled visit will be used
- If there are multiple assessments equidistant to the target study day
  - the average value will be used for laboratory parameters
  - the later assessment will be used for PerfO, PRO, HRQOL, and BMD by DXA scan

## 6.5. Methods for Handling Missing Data

#### 6.5.1. Adverse Event and Concomitant Medication Start Dates

If the end date is non-missing and the imputed start date is after the end date, the end date will be used as the start date.

- (1) Missing day only
  - If the month and year are the same as the month and year of the date of the start of study treatment, the date of the start of study treatment will be used.
  - If the month and year are before the month and year of the date of the start of study treatment, the last day of the month will be used.
  - If the month and year are after the month and year of the date of the start of study treatment, the first day of the month will be used.

- (2) Missing day and month
  - If the year is the same as the year of the date of the start of study treatment, the date of the start of study treatment will be used.
  - If the year is before the year of the date of the start of study treatment, 31 December will be used.
  - If the year is after the year of the date of the start of study treatment, 01 January will be used.
- (3) Missing day, month, and year
  - The date of the start of study treatment will be used.

